**Tool I: (Burn patient's assessment sheet)**

This tool will mainly aim to assess burn parameters (as extent, depth, and cause of burn), criteria of wound healing (as wound color, appearance of burn wound, signs of infection and presence of exudates). It will be comprised of three parts.

**Part I: Patient Sociodemographic data:** including:

- Personal characteristics: as Patients' age, gender, level of education, occupation, date of burn, date of admission, date of discharge and habits.
- Patient history including past and present history.

**Part II: Laboratory studies:**

- Complete blood count.
- Serum proteins.
- Electrolytes.

**Part III: Burn parameters:** This part will include data regarding: Site of burn, extent, cause, and depth.

**Part IV: Type of wound dressing:** Whether TTO or Conventional dressing.

**Tool II: (Burn wound follow up sheet)**

This tool will comprise two parts:

**-Morphological changes of the wound:**

This part will be used to assess burn wound healing, and determine signs of infection including signs of inflammation as wound color, presence of exudates (amount, color, and type), size, depth, edema, as well as frequency of dressing change.

- **Photographic pictures:**

Colored digital photographs will be taken three times to assess wound healing process (day of burn, each other day till healing and after one month)

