## **Method**

1. Written approval will be obtained from the hospital administrator and head of Burn Department, after explanation of the study aim.
2. The study tools will be developed by the researcher after review of relevant literature.
3. The developed tools will be submitted to 5 experts in the fields of plastic surgery &burn and Medical Surgical Nursing to test its content validity and necessary modification will be done accordingly.
4. Reliability of the tool will be tested.
5. Ethical considerations:
  - a. Patient's written informed consent will be obtained after explanation of the study aim.
  - b. Confidentiality, privacy and right of withdrawal will be assured.
  - c. Ethical committee approval will be obtained.
6. Pilot study will be conducted on 5 patients for testing, clarity, feasibility and applicability of the developed tools and modification will be done.
7. The study subjects meeting inclusion criteria and will be sequentially divided into two groups, the first group will receive conventional dressing (control group), and this dressing will be changed routinely once every other day. For the second group the wound will be dressed by TTO, which will be changed every other day till healing occurs. This frequency is advocated, since more frequent dressing change will interfere with granulation tissue formation.
8. All burn wound will be washed gently with Saline, and all open blister and loose non-viable tissue will be removed from the burn, intact blisters will be

left, and then the topical agents will be applied directly on wound. Burns involving body joints will be kept in functional position.

9. Initial assessment of all patients will be done using tool I. Subsequent assessment will be done on 4th, 14th, 21th of topical dressing agents use until the wound healing from both groups using tool II.
10. Colored digital photographs will be taken-if possible- to assess wound healing process at the (day of burn, each other day till healing, after one month)
11. Initial and ongoing assessment results for the conventional dressing, compared to TTO dressings, will be carried out using appropriate statistical methods.

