#### **Statistical Analysis Plan (SAP):**

Data will be analyzed using IBM SPSS software package version 23.0. The Shapiro-Wilk will be used to verify the normality of distribution of variables; Comparisons between groups for categorical variables will be assessed using Chi-square test (Monte Carlo or Fisher Exact). Student t-test will be used to compare two groups for normally distributed quantitative variables, Mann Whitney test will be used to compare two groups for not normally distributed quantitative variables, Friedman Test for multiple comparisons between the different periods in each group. Significance of the obtained results will be judged at the 0.5% level.

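### No outcome or time point is named to decide the healing question; 15 to 21 uncontrolled between-arm comparisons carry a false-positive chance of about 7–10% at the written 0.5% level, or 54–66% if 5% was meant

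*Combined protocol and SAP*

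**What the plan says.** The Aim of the study section poses a single comparison of two dressings on healing and gives no measure or time for it.

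Tool II is described as the instrument for assessing healing and for detecting infection. Its items are wound colour, then "presence of exudates (amount, color, and type), size, depth, edema, as well as frequency of dressing change". None is marked as primary.

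Method item 9 applies Tool II at the 4th, 14th and 21st (presumably days) "of topical dressing agents use until the wound healing from both groups using tool II". Method item 11 adds: "Initial and ongoing assessment results for the conventional dressing, compared to TTO dressings, will be carried out using appropriate statistical methods".

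The SAP lists tests by type of variable: "Comparisons between groups for categorical variables will be assessed using Chi-square test (Monte Carlo or Fisher Exact"), then "Student t-test will be used to compare two groups for normally distributed quantitative variables", with Mann-Whitney where normality fails. Its only reference to multiple comparisons is the Friedman test, which compares periods within each group. The threshold is given once: "Significance of the obtained results will be judged at the 0.5% level".

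**The concern.** One question is asked, but many answers are collected and nothing says which one counts. The SAP's between-arm tests each handle one variable at one time, and none combines visits. Followed as written, the plan lets a difference in any one attribute at any one visit be reported as a healing benefit. For example, a better wound colour at one visit could carry the conclusion while wound size shows nothing.

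The Friedman test does not help, because it looks at change over time inside each arm and does not limit errors in the comparison of arms. The stated significance level then describes a single test, not the chance of wrongly claiming that the dressings differ.

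**Working it through.** The documents state no family-wise error rate, so there is no figure of the plan's to reproduce. The only error rate given is the 0.5% level per test.

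**Inputs**
- Attributes (Tool II): wound colour, exudate, size, depth and oedema make 5. Splitting exudate into amount, colour and type makes 7. Dressing frequency is left out, because Method item 7 sets it to every other day in both arms.
- Visits (Method item 9): 3.
- Tests, if each attribute is compared at each visit: 5 × 3 = 15, or 7 × 3 = 21.
- Level per test: 0.005 as written; 0.05 as the alternative if the written value is a slip (assumption).

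**Independent tests, either direction:** chance of at least one false positive = 1 − (1 − α)^m.

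| Tests m | α = 0.005 | α = 0.05 |
|---|---|---|
| 15 | 1 − 0.995^15 = 7.2% | 1 − 0.95^15 = 53.7% |
| 21 | 1 − 0.995^21 = 10.0% | 1 − 0.95^21 = 65.9% |

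For 21 tests the expected number of false positives is 21 × 0.005 = 0.105, or 21 × 0.05 = 1.05. The 10.0% is about 20 times the per-test level of 0.5%.

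**Only results favouring tea tree oil** (two-sided tests assumed, so α/2 per test): 1 − (1 − α/2)^m.
- α = 0.005: 3.7% (m = 15) and 5.1% (m = 21), about half the figures above.
- α = 0.05: 31.6% (m = 15) and 41.2% (m = 21), about three-fifths of the figures above.

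**Correlated tests.** The documents give no correlations, so these are assumptions. Simulating 21 two-sided normal tests:

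| Correlation between visits / attributes | α = 0.005 | α = 0.05 |
|---|---|---|
| 0.3 / 0.1 | 9.8% | 63.6% |
| 0.5 / 0.3 | 8.8% | 56.3% |
| 0.7 / 0.5 | 6.9% | 44.2% |
| 0.8 / 0.7 | 4.9% | 31.9% |

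**Conservative exact tests.** For a binary item with 25 per arm and an assumed event rate of 20–50%, Fisher's exact test has a true size of about 0.19–0.26% at the 0.5% level and 2.2–3.3% at the 5% level. If all 21 tests were of this kind and independent, the chance would be about 4–5% and 38–50%.

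**When a chance finding becomes more likely than not:** m > ln 0.5 / ln(1 − α), which is 139 independent tests at 0.005 and 14 at 0.05.

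**The case against.** A reader might infer that a chance significant result is likely even if the dressings are equivalent. The documents do not support that. The only level they give is 0.5%, where 21 independent tests carry a 10% risk, far short of the 139 tests needed to pass one half. The stronger statement needs 5%, which the documents never state. Even at 5%, the two stronger correlation scenarios fall below one half.

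Four further objections have weight.
- Testing each attribute at each visit is an inference. The SAP names types of test, and Method item 11 leaves the methods open. It remains the natural reading, because no method that combines visits between arms is listed.
- The count of seven depends on splitting exudate, and the tools are still to be validated, piloted and modified. The lower count of 15 is therefore carried through the main calculation.
- Tool II also serves to detect infection, so not every item is a claim about healing.
- The either-direction figures overstate the risk of a false claim for tea tree oil in particular, and exact tests would lower it further. Both effects are shown in the working.

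These points reduce the size of the problem. None of them supplies a primary outcome, a deciding time point or between-arm error control.

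**Conclusion.** The concern holds, with moderate size at the written level. No outcome or time point decides the healing question, and about 15 to 21 comparisons could each carry the conclusion. With independent tests, the chance of at least one false positive in either direction is about 7–10% at 0.5%. That exceeds both the stated per-test level and a conventional 5%, but it is not a likely event. If 0.5% is a slip for 5%, the figure is 54–66%.

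These are upper-end values. They assume attribute-by-visit testing, independence and tests that hold their nominal size. Which of the two ranges applies cannot be settled from the documents, so the sponsor has to confirm the level.

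**What to change.** In the SAP:
1. Confirm whether the significance level is 0.5% or 5%.
2. Name one primary outcome: time from first dressing to complete wound healing, compared between arms with an effect estimate and 95% confidence interval. State that the conclusion on healing rests on it.
3. Make the Tool II attributes secondary, with one prespecified between-arm comparison per attribute across visits. Where a repeated-measures model is not workable, as for exudate colour or type, use one named visit. Because assessment runs only until healing, say how a healed wound is scored at later visits.
4. Apply Holm over the secondary attributes at the confirmed level. For seven attributes the first step is 0.05/7 = 0.0071 if the level is 5%, or 0.005/7 = 0.00071 if it is 0.5%. The two must not be mixed: 0.0071 is looser than the 0.005 now written.

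In Tool II, the investigators should define complete healing and record its date. Neither is there now: Tool I lists dates of burn, admission and discharge only, and photographs are taken only if possible. Dressings are changed every other day until healing, so the date can be known to within about two days.

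The cost is a healing definition, one added date field and a stricter threshold for any single secondary attribute. No extra visits are needed.

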## **Method**

1. Written approval will be obtained from the hospital administrator and head of Burn Department, after explanation of the study aim.
2. The study tools will be developed by the researcher after review of relevant literature.
3. The developed tools will be submitted to 5 experts in the fields of plastic surgery &burn and Medical Surgical Nursing to test its content validity and necessary modification will be done accordingly.
4. Reliability of the tool will be tested.
5. Ethical considerations:
  - a. Patient's written informed consent will be obtained after explanation of the study aim.
  - b. Confidentiality, privacy and right of withdrawal will be assured.
  - c. Ethical committee approval will be obtained.
6. Pilot study will be conducted on 5 patients for testing, clarity, feasibility and applicability of the developed tools and modification will be done.
7. The study subjects meeting inclusion criteria and will be sequentially divided into two groups, the first group will receive conventional dressing (control group), and this dressing will be changed routinely once every other day. For the second group the wound will be dressed by TTO, which will be changed every other day till healing occurs. This frequency is advocated, since more frequent dressing change will interfere with granulation tissue formation.
8. All burn wound will be washed gently with Saline, and all open blister and loose non-viable tissue will be removed from the burn, intact blisters will be

left, and then the topical agents will be applied directly on wound. Burns involving body joints will be kept in functional position.

9. Initial assessment of all patients will be done using tool I. Subsequent assessment will be done on 4th, 14th, 21th of topical dressing agents use until the wound healing from both groups using tool II.
10. Colored digital photographs will be taken-if possible- to assess wound healing process at the (day of burn, each other day till healing, after one month)
11. Initial and ongoing assessment results for the conventional dressing, compared to TTO dressings, will be carried out using appropriate statistical methods.

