### **Materials and method**

#### **Materials**

**Design:** An experimental design will be utilized.

**Setting:** The present study will be conducted at the burn unit, Alexandria Main University Hospital, Alexandria, Egypt.

**Subject:** A convenient sample of 50 patients admitted to burn unit suffering from second-degree burns will be included in the present study.

The fifty patients will be sequentially enrolled into two equal groups:-

- The first group (25 patients) will be managed conventional dressings (control group).

- The second group (25 patients) will be managed by local application tea tree oil (study group).

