**Patient's inclusion criteria will include:**

- Adults of both genders (18-60 years), able and willing to cooperate and communicate.
- Newly admitted to the study setting with recent 2nd degree burns whether superficial or deep ≤10%TSBA.
- Free of associated illness that affect wound healing as DM, immune disorder, or associated injuries.
- Free from pre-existing skin conditions such as eczema

**Tools:** Two tools will be used on this study:

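### Patients are assigned only sequentially, with no random sequence or concealment, so the next dressing can be foreseen and the unadjusted tests cannot correct for the result

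*Combined protocol and SAP*

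**What the plan says.** Allocation is described twice. Under Materials (Subject): "The fifty patients will be sequentially enrolled into two equal groups", with 25 patients in each. Under Method, item 7, subjects "will be sequentially divided into two groups, the first group will receive conventional dressing (control group". Neither place defines the rule. The design is labelled only as "An experimental design will be utilized", and recruitment is by convenience: "A convenient sample of 50 patients admitted to burn unit suffering from second-degree burns will be included in the present study". The text describes no sequence generation, concealment or stratification.

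The inclusion criteria admit second-"degree burns whether superficial or deep", of any extent up to 10% of body surface. Tool I, Part III records site, extent, cause and depth of the burn. Part IV records the dressing ("Whether TTO or Conventional dressing").

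For the comparison of arms the SAP states: "Student t-test will be used to compare two groups for normally distributed quantitative variables". It adds Mann-Whitney for non-normal variables and chi-square, Monte Carlo or Fisher, for categorical ones. The Friedman test is used within each group. No covariate or adjusted model is named; Method item 11 and the Results section refer only in general terms to suitable methods. On the threshold: "Significance of the obtained results will be judged at the 0.5% level".

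**The concern.** An unadjusted p-value speaks for a treatment effect only if the two arms are exchangeable at baseline. Random allocation provides that in expectation, and the test's error rate already allows for chance imbalance. It does not allow for a systematic shift that arises because the recruiter knows which dressing comes next. Such a shift pushes every between-group comparison in one direction.

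The opportunity is real here. A convenience sample, and a requirement that patients be able and willing to cooperate, leave discretion over whom to enrol. Mixing superficial and deep burns means that such choices can matter for healing. If sequentially means 25 controls and then 25 TTO patients, arm is also tied to calendar time, so any change in staff, season or case mix during recruitment becomes part of the apparent dressing effect.

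**Working it through.** **1. The plan's own figure.** 25 + 25 = 50, which agrees. No power, effect size or SD is given, so the sample size cannot be derived further.

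**2. How much can be foreseen.** Under alternation, all 49 assignments after the first are known. Under 25-then-25, all 50 are known. By comparison, with a random 25/25 list whose future entries are concealed, a recruiter who knows every past assignment guesses right about 58% of the time.

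**3. Effect on the planned t-test.** Inputs from the documents: 25 per arm, and the written level of 0.005. Assumed: two-sided testing; 0.05 as a second level; no true effect; superficial burns heal at mean 13 d (SD 3), deep burns at mean 17 to 21 d (SD 4). Spurious gain = (difference in deep share) × (deep mean − superficial mean). Rejection rates are from 40,000 simulated trials per row.

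| Chance of deep burn, control / TTO | Deep mean | Spurious TTO gain | Rejects at 0.05 | Rejects at 0.005 |
|---|---|---|---|---|
| 50 / 50 | 17–21 d | 0 | 4.9–5.1% | 0.4–0.5% |
| 60 / 40 | 17 d | 0.20 × 4 = 0.8 d | 10.7% | 1.8% |
| 60 / 40 | 21 d | 0.20 × 8 = 1.6 d | 18.8% | 4.2% |
| 65 / 35 | 17 d | 0.30 × 4 = 1.2 d | 18.3% | 3.8% |
| 65 / 35 | 21 d | 0.30 × 8 = 2.4 d | 36.3% | 11.6% |

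Mann-Whitney behaves alike at 0.05: 10.2–19.8% at 60/40 and 18.4–35.5% at 65/35.

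*Cross-check of the 60/40, 17 d row.* Variance in an arm = (deep share × 4²) + (superficial share × 3²) + (product of the shares × 4²).
- Control: 9.6 + 3.6 + 3.84 = 17.04.
- TTO: 6.4 + 5.4 + 3.84 = 15.64.
- Average 16.34, so SD 4.04, and the shift is 0.8 / 4.04 = 0.20 SD.

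The exact noncentral t (48 df, noncentrality 0.2 × √(25/2) = 0.71) gives 10.7% and 1.7%, in agreement. For other assumed shifts it gives 18.0% and 3.7% at 0.3 SD, and 41.0% and 13.3% at 0.5 SD.

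**4. A binary outcome.** Healed by day 14, a scheduled assessment (Method, item 9). At 60/40 the healed shares are 39% v 47% (deep mean 17 d) or 28% v 39% (21 d), control v TTO.
- Uncorrected chi-square: 10.5–15.5% at 0.05 (1.4–2.8% at 0.005), against 5.6–6.4% (0.5–0.6%) with no shift. At 65/35: 16.2–27.6% (2.9–6.6%).
- Fisher at 60/40: 6.0–8.8% at 0.05, against 2.7–3.2% with no shift. This is lower in absolute terms but still two to three times its own null rate.

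**5. What adjustment would do.** A linear model with depth as covariate, in the same scenarios, rejects 4.5–5.2% at 0.05 and 0.45–0.5% at 0.005. It removes the part due to depth, but not selection on anything unrecorded.

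**6. Calendar time.** Enrolment order 1 to 50 has SD √((50² − 1)/12) = 14.43. Under 25-then-25 the arms' mean order differs by 25, so r = 0.5 × 25 / 14.43 = 0.866. Variance inflation is 1/(1 − 0.866²) = 4.0, and 25 per arm is worth about 6.2. Under alternation the mean order differs by 1, so r = 0.035 and inflation is 1.00.

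**The case against.** The strongest reply is that foreseeability is inferred: sequential enrolment may mean only consecutive accrual, with the allocation method left unstated. The wording under Materials could bear that. Method item 7 cannot, because there patients are sequentially *divided* into the groups. In any case the plan supplies no other rule.

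Other points stand in part:

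- **Steering is not shown, only left open.** If half of eligible patients have deep burns, reaching 60/40 means turning away a third of the unfavoured type, about 60 eligible patients for 50 places; 65/35 means refusing 46%, about 65 patients. The direction favouring TTO is also an assumption.
- **Milder cases do little harm.** A fixed 15 v 10 split of deep burns gives 7.2–8.3% at 0.05 and 0.4–0.7% at 0.005, the latter close to nominal. With 25 of 50 burns deep, a gap of five or more arises by chance in 25.8% of unstratified 1:1 randomisations (hypergeometric), so a gap by itself does not show steering.
- **Tool I already records depth and extent,** so these can be examined and adjusted for. But no such adjustment is planned, and unrecorded factors would remain.
- **The supplied text never calls the trial randomised,** so nothing is contradicted. The title page was not available; a label there would supply neither a sequence nor concealment.

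**Conclusion.** The concern holds and should be fixed before the comparison is relied on. Three facts need no assumed input: sequential assignment is the only rule, no random sequence or concealment is given, and every planned between-group test is unadjusted. That the next arm is foreseeable follows from either plain reading of the rule.

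The size of the bias cannot be known from the documents. Under the stated assumptions, a 60/40 to 65/35 shift in the chance of a deep burn produces a spurious gain of 0.8 to 2.4 days. It raises the t-test's false-positive rate from 5% to between 11 and 36%, or from 0.5% to between 1.8 and 11.6% at the written level. The finding does not depend on which level was intended. It is a weakness of design, not an inconsistency, and it affects every comparison between the dressings.

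**What to change.** **If allocation has not started.** Replace the sequential rule under Materials and in Method item 7 with text such as:

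> Patients are randomised 1:1 from a computer-generated list in permuted blocks of varying size, stratified by burn depth (superficial or deep). Assignments are kept in numbered, opaque, sealed envelopes prepared by a person not involved in enrolment. Each is opened only after consent and completion of Tool I, Parts I to III.

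Part IV of Tool I records the dressing, so it is completed after opening. An equivalent concealed scheme is acceptable. Stratification is a refinement; concealed randomisation is the essential element.

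**If patients have already been allocated.** State which sequential rule was used, describe the study as non-randomised, base the conclusion on an analysis adjusted for burn depth and percentage of body surface burned, and limit causal wording. Under 25-then-25, adjusting for enrolment date costs a four-fold variance, so calendar confounding cannot be reliably removed and should be declared a limitation. Under alternation, date adjustment is harmless but adds little.

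**Cost.** A short amendment, one list, two sets of envelopes (one per depth stratum), and some time from someone outside enrolment. With stratified blocks the 25/25 split becomes approximate. No extra patients or visits are needed, and the fallback uses data that Tool I already collects.

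### The Tool II wound sheet is never completed before treatment, so oedema and graded exudate have no stated baseline, and colour, exudate presence and size have none on the follow-up instrument

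*Combined protocol and SAP*

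**What the plan says.** Method item 9 splits the assessments between two forms. "Initial assessment of all patients will be done using tool I"; later assessments fall on the 4th, 14th and 21st "of topical dressing agents use until the wound healing from both groups using tool II". No unit is printed for these times; I read them as days.

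The introduction to Tool I says that it covers burn parameters and "criteria of wound healing (as wound color, appearance of burn wound, signs of infection and presence of exudates". Its listed parts are sociodemographic data and history, laboratory studies, burn parameters, and type of dressing. The burn-parameter part is described as "Site of burn, extent, cause, and depth".

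Tool II has two parts. The morphology part covers wound colour and "presence of exudates (amount, color, and type), size, depth, edema, as well as frequency of dressing change". The photographic part is timed at "day of burn, each other day till healing and after one month", and Method item 10 makes the photographs conditional on feasibility.

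Method item 11 plans to compare initial as well as ongoing results between the dressings. The SAP names a "Friedman Test for multiple comparisons between the different periods in each group" but does not list the periods, and it plans no baseline-adjusted comparison of the arms.

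**The concern.** The wound features used to judge healing are defined in Tool II, and nothing schedules that sheet before the first dressing. A change from the starting state can be estimated only if the same item is recorded in the same way at the start and at follow-up.

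This matters more here than in a randomised trial. The 50 patients are a convenience sample divided sequentially into two groups of 25, and both superficial and deep second-degree burns are eligible. If one group began with more oedema or heavier exudate, the difference could still be present at the first follow-up and be read as an effect of the dressing. For items without a baseline, it could be neither checked nor adjusted for. A pre-treatment observation that was not made cannot be recovered later.

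**Working it through.** **Step 1: coverage before treatment, item by item.** The plan gives no figure to reproduce, so the check compares the stated contents and timing of the two tools.

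| Tool II item | Named in Tool I's aim | In Tool I's listed parts | Baseline on the follow-up sheet |
|---|---|---|---|
| Wound colour | yes | no | no |
| Exudate, presence | yes | no | no |
| Exudate: amount, colour, type | no | no | no |
| Size | burn extent | burn extent | no |
| Depth | yes | yes | no |
| Oedema | no | no | no |

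The items fall into three groups.
- Oedema and graded exudate have no stated baseline anywhere.
- Colour and presence of exudate are promised by Tool I's aim but have no field in its parts. Even if a field were added, presence of exudate does not match a grading of amount, colour and type.
- Depth and burn extent are recorded at the start. The plan does not say that extent and Tool II size are measured in the same way.

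Item 11's comparison of initial with ongoing results therefore lacks matching data for several items. If the Friedman periods are the Tool II times, all of them fall after treatment has begun; the SAP does not say.

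**Step 2: how far a starting difference carries over.** Assume a continuous item with equal SD at both times, a linear relation with correlation r, and no treatment effect. A starting difference of k SD then gives an expected follow-up difference of r × k SD. With 25 per arm, the standard error of a purely chance starting difference is √(2/25) = 0.28 SD. A starting difference of that size carries over as 0.2 × 0.28 = 0.06 SD, 0.5 × 0.28 = 0.14 SD, or 0.7 × 0.28 = 0.20 SD. Sequential allocation does not limit k to what chance alone would produce.

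**Step 3: precision.** Adjusting for a baseline with correlation r reduces the residual variance by the factor 1 − r², so a difference of d SD behaves like d/√(1 − r²). Two-sample t-test power uses n = 25 per arm, 48 degrees of freedom and noncentrality [d/√(1 − r²)] × √(25/2). With d = 0.7 (assumed) and r = 0.5, the effective difference is 0.7/√0.75 = 0.808 and the noncentrality is 0.808 × 3.536 = 2.86.

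| r (assumed) | Effective d | Power, two-sided 5% | Power, two-sided 0.5% (as printed in the SAP) |
|---|---|---|---|
| 0 (no adjustment) | 0.700 | 0.679 | 0.332 |
| 0.2 | 0.714 | 0.697 | 0.350 |
| 0.3 | 0.734 | 0.720 | 0.375 |
| 0.5 | 0.808 | 0.800 | 0.474 |
| 0.7 | 0.980 | 0.924 | 0.697 |

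The calculation ignores the one degree of freedom spent on the covariate and any loss from baseline imbalance between the arms. It applies to continuous items only.

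**The case against.** A reader might infer that neither arm has any baseline for size, colour, exudate or oedema. The documents do not support that.

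- Tool I's stated aim names colour, appearance, infection signs and presence of exudate, and Tool I is applied to every patient at the start.
- Extent and depth are listed fields, and eligibility already uses extent (a limit of 10%).
- Photographs belong to Tool II and begin on the day of burn, so only the morphology part of Tool II starts late.
- The tools are still to be developed, reviewed by five experts and piloted, so the listed parts may be a summary and not the final form.
- Item 11 leaves a starting imbalance in extent or depth open to comparison, so it would be wrong to say that no starting difference could be detected or adjusted for.
- That the Friedman test covers only times under treatment is an inference, because the periods are not listed.

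All of this stands, and it narrows the point. It does not remove it. An aim without a matching field does not ensure that the item is recorded. Photographs taken only where feasible, with no scoring described, do not supply an oedema grade or an exudate amount. Oedema and graded exudate are named nowhere before treatment.

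The power figures are also open to challenge. They depend on an assumed correlation, the gain is small at r = 0.2 or 0.3, and several of the items are graded or categorical. The point does not depend on them.

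**Conclusion.** The concern holds in limited form. The Tool II morphology sheet has no scheduled completion before treatment. Oedema and exudate amount, colour and type have no stated baseline. Colour, presence of exudate and size have none on the follow-up instrument. Whether Tool I will capture colour and exudate is unresolved, because its aim and its listed parts disagree.

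The main consequence is possible bias at first follow-up under sequential allocation. The documents do not show that an imbalance exists, and its size cannot be derived from them. The precision gain is secondary: between 2 and 25 percentage points of power at two-sided 5% (68% to 70% at r = 0.2, 68% to 92% at r = 0.7), for a continuous item with an assumed 0.7 SD difference. The change is worth making because it is cheap and cannot be made after treatment has begun.

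**What to change.** 1. Change Method item 9 so that Tool II is also completed in both arms at the initial assessment, before the first topical application.
2. In the SAP, list the Friedman periods and name that assessment as the first.
3. Compare the arms at follow-up adjusting for the baseline value of the same item and for burn depth: ANCOVA for continuous items, ordinal regression for graded items.
4. Reconcile Tool I's stated aim with its listed parts, and say whether burn extent and Tool II size are the same measure.

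The cost is one extra form per patient (50 forms) at an assessment that already takes place, and slightly more analysis. Adjustment reduces bias from the measured starting differences only. It does not cure the allocation bias itself, which needs separate attention.
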